# A non-invasive intervention (BreEStim) for management of phantom limb pain (PLP) after limb amputation

# Protocol (CPHS HSC-MS-20-1032)

1. Protocol Title: A non-invasive intervention (BreEStim) for management of phantom limb pain

(PLP) after limb amputation PI: [name], PhD

Co-Investigators: [name]; [name], MS

Study Coordinator: not identified Population: amputee subjects Number of Sites: single site

Study Duration: planned for 3 years Subject Duration: estimated 64 subjects

# 2. Specific aims and research questions:

The overall goal of this project is to compare the effectiveness of innovative intervention of breathing-controlled electrical stimulation (BreEStim) and conventional electrical stimulation (EStim) in management of neuropathic phantom limb pain in patients after limb amputation.

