### 2) The proposed activities further the purposes of the Act

The intention of the Rehabilitation Act of 1973 is to promote the right of individuals with disabilities. They constitute one of the most disadvantaged groups in society, to live independently, contribute to society, pursue meaningful careers, and enjoy full inclusion and integration into all aspects of mainstream American society. It ensures that the U.S. government plays a leadership role in promoting the employment of individuals with disabilities.

The proposed project seeks to develop an alternative, noninvasive, and non-pharmacological treatment (BreEStim) for phantom limb pain management. Comparisons of analgesic effects between BreEStim and conventional electrical stimulation technique (EStim) will demonstrate superior analgesic effects by BreEStim. This has been shown in our recent preliminary study using BreEStim for neuropathic pain after spinal cord injury(Li et al. 2016; Karri et al. 2018a; Li et al. 2018). With the evidence and results to be obtained from this project, we will be able to provide strong clinical and laboratory evidence that this treatment will provide more effective and longer lasting analgesic effects for these patients, and improve general well-being of these patients. As mentioned earlier, quality of life and unemployment status is related to the severity of PLP(Whyte and Carroll 2002). Therefore, the proposed activities will obviously benefit a large population of patients, who may experience different levels of impairment and disability, by reducing their pain, emotional tension, thereby maintaining and enhancing quality of life and employment for these patients and meanwhile reducing the burden on caregivers. In this manner, the proposed activity will clearly increase these patients'

IRB NUMBER: HSC-MS-20-1032
UTHealth
IRB APPROVAL DATE: 12/03/2020
The University of Texass

2

ability to achieve the stated mandates of the Rehabilitation Act. The proposed activities, therefore, clearly further the goals of the Rehabilitation Act.

- The proposed project will have beneficial impact on the target population.

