# Non-pharmaceutical modalities (acupuncture, TENS, aversive electrical stimulation) for **PLP** management

Electrical stimulation (TENS) for pain Various neurostimulation techniques, including transcutaneous electrical nerve stimulation (TENS) (Norrbrink Budh and Lundeberg 2004), spinal cord stimulation (Finnerup et al. 2001b), deep brain stimulation (Murphy and Reid 2001), and transcranial direct current stimulation (Freqni et al. 2006) have been used for management of neuropathic pain. We are particularly interested in non-invasive stimulation that is relevant to our study – TENS.

TENS is noninvasive, inexpensive, safe and easy to use. TENS for pain relief was fully accepted by the medical field after the publication by Wall and Sweet in 1967 (Wall and Sweet 1967) which provided experimental evidence supporting the gate theory of pain (Melzack and Wall 1965). TENS is usually applied at varying frequencies, intensities and pulse duration of stimulation for a prescribed treatment time. Frequency of stimulation is broadly classified as high frequency (>50Hz) or low frequency (<10Hz) or bursts of high frequency stimulation at a much lower frequency. Intensity is determined by patient's response as either at the sensory level or motor level TENS. With the sensory level TENS, the stimulation intensity (voltage, or amplitude) is increased until the patient feels a comfortable tingling/tapping sensation without muscle contraction (twitching). With the motor level TENS, the intensity is increased to produce a motor contraction, but electrical stimulation is not noxious or painful. The usual TENS settings are high-frequency and low-intensity, or low-frequency and high-intensity. TENS has been applied to a variety of pain conditions, including phantom limb pain. Overall, the clinical effectiveness of TENS is controversial (see Review(Sluka and Walsh 2003; Mulvey et al. 2010; Johnson and Bjordal 2011)).

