Acupuncture and electro-Acupuncture for pain Acupuncture is a special kind of neurostimulation that is applied to acupuncture points (Acupoints). Acupoints are special points located in the periphery but are connected to internal organs including spinal cord and brain, following different channels, according to traditional Chinese medicine. Systematic investigation on mechanisms of acupuncture started in 1950s in China (Han 2004). Evidence on clinical effectiveness and mechanisms has accumulated over decades in Western Medicine literature (Hui et al. 2000: Han 2004: Yoo et al. 2004; Cho et al. 2006; Dhond et al. 2008). Acupuncture for pain relief via the release of endogenous opioids has been well accepted in Western Medicine. Modification to traditional acupuncture needle has been made (Han et al. 1981; Han 2004). It has been replaced by a surface electrode (or equivalent). When a specialized electrode is placed over traditional acupoints, electrical stimulation is delivered. This modification has been termed electroacupuncture. Needle acupuncture and electroacupuncture are both effective in analgesia (Wan et al. 2001; Huang et al. 2002). The effect of electroacupuncture is usually reliable, but dependent on intensity and frequency of delivered electrical stimulation: different frequency of electrical stimulation generates different endogenous opioids, and the analgesic effect is naloxonereversible (Huang et al. 2002; Han 2004).

Aversive electrical stimulation to acupuncture points Theoretically, analgesic effects are anticipated to be strengthened if different mechanisms of treatment are delivered at the same time. Following this line, repetitive aversive electrical stimulation delivered to acupoints is expected to have combined effects: 1) habituation to aversive stimulation as described above; 2) analgesic effect secondary to the release of endogenous opioids secondary to stimulation of acupuncture points. Therefore, in combining different mechanisms (the release of endogenous opioids, habituation), aversive electrical stimulation to acupoints is theoretically anticipated to produce significant analgesic effects.

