### Specific Aim 3: to examine the long-term effect of BreEStim on neuropathic PLP

It is critical to know whether patients will tolerate electrical stimulation and the induced analgesic effect will diminish or the effect will accumulate if patients receive BreEStim repetitively over time, before it is translated into a therapeutic device. It is hypothesized that the BreEStim treatment will produce a greater analgesic effect than the convention electrical stimulation (EStim) treatment in patients after traumatic amputation over a course of 2 weeks (10 consecutive workdays). We will examine the hypothesis by comparing electrical pain threshold and effectiveness in pain reduction between BreEStim and EStim in patients after traumatic amputation of one limb. The analgesic effect will be assessed by pain reduction in visual analog scale and quantitative measurement of electrical sensation and pain thresholds. The effect on general well-being and change in pain medication will be assessed.

IRB NUMBER: HSC-MS-20-1032 UTHealth IRB APPROVAL DATE: 12/03/2020

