# D. The data collection and measurement techniques are appropriate and effective

# Experimental Design

The overall research design is a within-group, randomized controlled study to compare analgesic effects between EStim and BreEStim (single-session in Exp 1, long-term intervention in Exp 3), between BreEStim120 and BreEStim240 (Exp2). We prefer this within-group comparison because 1) pain, by nature, is a subjective perception, it is difficult to control (physical, social, psychological) multi-factors between two groups; 2) It will be fair that all subjects receive the innovative intervention, which is superior to regular electrical stimulation according to our pilot data; 3) according to our recent BreEStim study in patients with spinal cord injury, the duration of analgesic effect was 15 hours after one-session of BreEStim treatment. An interval of one week for washout should be sufficient for Exp 1 & 2. The washout interval will be 2 weeks for Exp 3. It is our experience with subjects with spinal cord injury that an interval of 7 days is sufficient for subjects to return to their baseline after BreEStim treatment. (Li et al. 2016; Karri et al. 2018b; Li et al. 2018) However, we did notice that one subject with post-amputation PLP had carry-over effect for one month(Li et al. 2012a). We plan to screen these patients with longlasting carry-over effects. These patients will be excluded from the subject should this happen.

In Experiment 1, we plan to use our recent BreEStim and EStim protocols (Li et al. 2013; Li et al. 2014; Li et al. 2016) to measure mechanical sensation threshold, thermal (cold/warm detection, cold/hot pain) thresholds, and electrical sensation and pain thresholds in the treatment limb and contralateral limb. The same group of subjects will receive both BreEStim and EStim at a randomized yet balanced order with at least 7 days apart. The same amount of electrical stimulation (120 stimuli) will be given during both BreEStim and EStim. The purpose of this aim is to investigate whether BreEStim could have better analgesic effect than EStim in amputee subjects with chronic phantom limb pain as we observed in healthy subjects. We expect increased electrical pain thresholds in both limbs after BreEStim because of its central desensitization effects.

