In the EStim condition, subjects will also wear the face mask as in the BreEStim condition. The main difference is that subjects will be breathing automatically and comfortably and electrical stimulation pulses will be delivered randomly. The pulses will be programmed to randomly deliver at about every 2 seconds (between 1.9 seconds and 2.1 seconds). The pulse width will be the same at 0.1ms. Similarly, subjects control the intensity of electrical stimulation. For both BreEStim and EStim, they are strongly encouraged to increase the intensity to be painful yet tolerable gradually from their pain threshold. The level of pain with painful stimulation will be 7 on the 0-10 VAS scale. The purpose is to make the intensity of electrical stimulation comparable between two conditions. According to previous studies, the intensity is comparable between BreEStim and EStim(Li et al. 2013; Li et al. 2014). The intensity of electrical stimulation will be recorded during the course of treatment.

Two interventions (BreEStim vs. EStim) will be given to the same subject on a different day with at least 7 days apart. As in previous studies(Li et al. 2013; Li et al. 2014), a total of 120 electrical stimuli will be delivered for each intervention. The order of interventions will be randomized and balanced across subjects. Both interventions will be given at the same time of the day, as determined by subject's schedule. It is important to emphasize that subjects will be explicitly instructed to maintain the same pain regime even they feel that treatment has helped in pain reduction, such that pain reduction is mainly related to BreEStim or EStim.

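### EStim is called conventional stimulation but is delivered as deliberately painful stimulation, so a positive result supports superiority over that comparator only, not over conventional or regular stimulation

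*Combined protocol and SAP*

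**What the plan says.** The overall goal in section 2 is to "compare the effectiveness of innovative intervention of breathing-controlled electrical stimulation (BreEStim) and conventional electrical stimulation (EStim) in management of neuropathic phantom limb pain". The same label appears in section 3(a), both under the need and target population and in the list of beneficial impacts. Under the heading on the purposes of the Act the result is announced in advance: "Comparisons of analgesic effects between BreEStim and conventional electrical stimulation technique (EStim) will demonstrate superior analgesic effects by BreEStim". Specific Aim 3 hypothesises that BreEStim "will produce a greater analgesic effect than the convention electrical stimulation (EStim) treatment". The Experimental Design section justifies giving every subject BreEStim, "which is superior to regular electrical stimulation according to our pilot data".

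The experimental setup section defines what the EStim arm receives. Single 0.1 ms pulses are given every 1.9 to 2.1 seconds through electrodes over the median nerve at the wrist, above two acupuncture points that are stimulated in both conditions. Subjects control the intensity, and for both interventions "they are strongly encouraged to increase the intensity to be painful yet tolerable gradually from their pain threshold". The target is 7 on the 0-10 VAS, and the stated purpose is to make intensity comparable between conditions. For Experiment 3 the setup is described as similar, intensity is raised as tolerated, and aversiveness is said to be part of the treatment strategy.

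The review of non-pharmaceutical modalities describes TENS at two intensity levels. The sensory level is comfortable. For the other: "With the motor level TENS, the intensity is increased to produce a motor contraction, but electrical stimulation is not noxious or painful". The same review says that stimulation becomes aversive or noxious once it is felt as pain, and it covers aversive stimulation at acupuncture points under its own subheading: "aversive electrical stimulation to acupoints is theoretically anticipated to produce significant analgesic effects".

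**The concern.** A comparator's label fixes what a positive result is taken to mean. The goal, the Aim 3 hypothesis and the announced conclusion all name conventional or regular electrical stimulation. The arm delivered is stimulation that the protocol's own classification calls aversive, matched in intensity to the experimental intervention. If BreEStim wins, the report as planned would state superiority over something that no subject received.

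The direction of the error cannot be predicted from the documents. If painful stimulation at acupuncture points relieves pain by itself, as the review expects, the measured advantage could be smaller than against a non-painful comparator. If EStim sensitises, as the cited study in healthy subjects suggests (electrical pain threshold fell after EStim), the advantage could be larger.

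**Working it through.** The plan states no figure on this point, so the check sets the sections side by side, with some small arithmetic.

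1. **Pulse rate.** The interval is 1.9 to 2.1 s (experimental setup, EStim condition). Rate = 1/interval: 1/2.1 = 0.48 and 1/1.9 = 0.53 pulses per second. This lies in the low-frequency class of the TENS description (below 10 Hz). Frequency is therefore not what separates EStim from that description.

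2. **Intensity.** The TENS description gives a comfortable level and a motor level that is not painful. EStim in Experiment 1 is 7 on a 0-10 pain scale. In Experiment 3 no target rating is stated, but the stimulation is intended to be aversive, which the protocol defines as felt as pain. In both experiments EStim falls in the protocol's aversive class.

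3. **Do the stated reasons for BreEStim's advantage separate the two arms?** Section 3(a) credits BreEStim, as compared with conventional stimulation, with the following.
   - *An electroacupuncture effect and an electrical stimulation effect.* Experiment 1 states that the same acupuncture points are stimulated in both conditions. Both arms receive the same number of stimuli: 120 each in Experiment 1, and 240 per session in Experiment 3.
   - *Habituation to aversive stimuli.* Both arms are painful. The protocol argues that effortful inhalation may strengthen habituation, so the degree may differ, but the mechanism is open to both.
   - *Active involvement of the patient, including control of intensity.* Subjects control intensity in both arms. Involvement through breathing is specific to BreEStim.
   - *Tolerance of higher intensity.* Intensity is deliberately made comparable, and the note to Figure 2 reports comparable intensity in healthy subjects.

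   Most of these features are shared or matched, so the rationale describes a comparator different from the one delivered.

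4. **What does differ?** In BreEStim the subject makes fast, strong, deep inhalations and each pulse is triggered by the airflow. In EStim the subject breathes automatically and pulses arrive at random within the interval. Two things change together: effortful breathing and trigger timing. This trial has no breathing-only arm; that comparison was made only in an earlier study of healthy subjects.

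5. **Do the pilot data bridge the gap?** The Experiment 1 pilot (3 patients) gives VAS falls of 5.3 - 3.2 = 2.1 after BreEStim and 4.9 - 4.1 = 0.8 after EStim, a difference of 1.3. It is reported as a test of the same protocol, so it carries no information on non-painful stimulation.

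6. **Extent.** BreEStim is compared with EStim in Experiments 1 and 3: 16 + 30 = 46 of 64 subjects (section 5). Experiment 2 (18 subjects) compares two doses of BreEStim and is not affected. The 46 is the number of subjects in contrasts that carry the label; it does not measure bias or lost power.

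**The case against.** The strongest defence is that *conventional* is shorthand, fully specified in the setup section. Timing, pulse width, site, painful intensity and the reason for matching are all given, so a careful reader knows what EStim is. Specific Aim 1, the stated purpose of Experiment 1 and the analysis section say EStim without the adjective, and much of the loose wording sits in background text. The heading of the modalities review also lists aversive stimulation beside TENS and acupuncture. This limits the point to labelling and scope. It does not remove it, because the label also stands in the overall goal, the Aim 3 hypothesis and the announced conclusion.

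A reader might infer several stronger things that the documents do not support:

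- *That EStim is meant to be TENS, or that the trial claims superiority over TENS.* The protocol never equates the two and makes no such claim. It says only that TENS is relevant and that its effectiveness is controversial.
- *That EStim stands in for usual care.* Section 3 gives drug treatment as the standard of care.
- *That the control is invalid.* It is a deliberate and reasonable match on number of stimuli and intensity.
- *That the 7 of 10 target governs Experiment 3.* It is explicit only in the Experiment 1 procedure.
- *That a positive result would isolate the breath trigger.* The arms also differ in effortful breathing.

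**Conclusion.** The point holds as one of label and scope of conclusion. Experiments 1 and 3 can show whether effortful inhalation combined with breath-triggered delivery adds to painful stimulation that is not breathing-controlled. They cannot show that BreEStim is superior to conventional or regular electrical stimulation, because neither experiment includes an arm designed to be non-painful. No numerical bias is claimed, and the within-trial contrast, sample size and analysis are unaffected.

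The conclusion assumes that the protocol's own account of usual TENS settings and of aversive stimulation is a fair guide to what a reader will take *conventional* to mean, since the protocol does not define the word. If the sponsor means only stimulation that is not controlled by breathing, the text should say so, and the same rewording serves.

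**What to change.** Change wording only:

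1. In section 2, section 3(a) (need and target population, purposes of the Act, beneficial impacts), Specific Aim 3 and Experimental Design, describe the comparator as painful, non-breathing-controlled stimulation with the same number of stimuli and intensity adjusted by the subject to tolerance. Mention the target pain rating only for Experiment 1, where the protocol states one.
2. Limit the planned conclusion of Experiments 1 and 3 to the combined effect of effortful inhalation and breath-triggered delivery over such stimulation.
3. Remove the claim of superiority over *conventional* or *regular* stimulation, and revise the listed advantages in section 3(a) so that features shared or matched in EStim are not credited to BreEStim alone.
4. Reconcile section 7, which tells subjects to raise intensity to a level that may feel comfortable, with the setup section, which asks for a painful level. The two instructions conflict.

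Procedures, number of subjects and analysis stay as they are. The cost is a protocol text revision and a narrower headline claim.

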# 3. Background/literature review, Justification and Significance:

#### a) Importance of the problem

### 1) The need and target population

In the United States, there are approximately 1.7 million people living with limb loss(Ziegler-Graham et al. 2008). It is estimated that one out of every 200 people in the U.S. has had an amputation(Adams et al. 1999). Limb amputation could lead to three non-exclusive phenomena, including phantom limb pain (painful sensation from the absent limb, i.e., phantom limb), phantom limb sensation (any sensation in the absent limb, except pain), and stump pain (pain localized in the residual limb) (Nikolajsen and Jensen 2001). Phantom limb pain (PLP) is a complex condition that is caused by peripheral nerve damage from amputation. Similar to neuropathic pain from other etiologies (e.g., spinal cord injury), PLP is characterized by spontaneous and ongoing pain, described as burning, shooting, prickling or electrical, and/or pain in response to innocuous stimuli (allodynia) and exaggerated pain in response to noxious stimuli (hyperalgesia) (Bennett 2010). PLP has increasingly been recognized as an important contributor to suffering, poor rehabilitation outcomes, reduced quality of life, and employment status of the persons with PLP after amputation. This is because of the following facts.

- PLP is very common(Werhagen et al. 2004). About 60-80% amputees have PLP at 2 years post-amputation (Jensen et al. 1985; Ephraim et al. 2005).
- PLP does not resolve over time. Phantom pain does not change after 6 months post-amputation (Jensen et al. 1985).
- PLP is difficult to manage (Woolf and Mannion 1999). Currently, pharmacological management is the standard of care for PLP. According to a Cochrane review(Alviar et al. 2011), there are 6 groups of medications with different pharmacological mechanisms have been the pharmacological medications demonstrated trends in short-term analgesic efficiency.

The University of Texas
Health Science Center at Houston

morphine. But the studies lacked long-term efficacy and safety outcomes. Furthermore, more studies were not specifically for PLP(Hall and Eldabe 2018). Nevertheless, pharmacological interventions are often associated with side effects, such as addiction, withdrawal, and constipation, etc.

- PLP is related to poorer physical, psychological and social functioning(Stormer et al. 1997; Norrbrink Budh et al. 2005; Jensen et al. 2007); More importantly, it was found that employment status was related to the intensity of PLP. Unemployed amputees reported higher levels of PLP and lower levels of prosthesis use(Whyte and Carroll 2002).
- These challenges in treating neuropathic PLP likely contribute to opioid overuse and the opioid epidemics(Manchikanti et al. 2012). The U.S. Senate passed the Comprehensive addition and Recovery Act (CARA), which takes incremental steps to combat the epidemic. It was signed into law in July 2016(CARA 2016). To combat this epidemic and to help manage PLP in particular, it is critically important to develop non-pharmacological interventions.

Alternative, non-pharmacological treatments have been tried for management of neuropathic pain in the target population. Acupuncture and various electrical stimulation techniques have been used clinically and have demonstrated some success. Based on our pioneering discovery that human voluntary breathing could have systemic effects, including pain reduction(Li and Rymer 2011a), we propose an innovative treatment – Breathing-controlled electrical stimulation (BreEStim) for neuropathic pain management. Briefly, in the BreEStim treatment, a single-pulse electrical stimulation is delivered to peripheral nerve(s) when patients are taking a fast, strong, and deep inhalation, similar to a deep breath but faster and stronger. Patients control the intensity of electrical stimulation, to increase the intensity as tolerated gradually. As compared to conventional electrical stimulation (EStim), this patient-centered treatment of BreEStim increases its analgesic effectiveness by integrating various internal coping mechanisms, including voluntary and active involvement of patient in their own care, electroacupuncture effect, electrical stimulation effect, neurobehavioral modulations (habituation to aversive stimuli, and activation of the reward system), resulting in increased pain threshold and pain tolerance (Li et al. 2013). Our pilot data have demonstrated that BreEStim has better effectiveness in pain reduction in patients with above-the-knee amputation in our previous case report (Li et al. 2012a).

The proposed research will further compare the effectiveness of BreEStim and EStim in management of neuropathic pain in patients with PLP. This well-coordinated clinical study by an established scientist-physician team will provide direct evidence of clinical effectiveness of BreEStim in phantom limb pain management. As such, an alternative and effective non-pharmacological treatment of PLP could be developed.

